1. BACKGROUND

The burden of Chronic insomnia (CI) is high, with point prevalence ranging between 6% and 10% (2–4). Apart from deterioration in the quality of life of each patient, their families, and friends, CI imposes also a non-negligible social and economic burden. This burden includes resources used for treatment, as well as reduced or lost work productivity. CI impacts labor by means of time, efficiency, and results in productive work activities losses and may even lead to loss of employment. The treatment of choice is a multicomponent treatment, cognitive-behavioral therapy for insomnia (CBT-I). CBT-I consists of sleep restriction, stimulus control, various relaxation techniques, sleep hygiene education, and cognitive restructuring of maladaptive beliefs and concerns about sleep. Nevertheless, time-consuming treatment courses and the lack of trained CBT-I clinicians cause difficulties in the implementation of these methods. Thus, developing innovative automatized and remote methods of performing CBT-I, such as internet-delivered CBT-I (iCBT-I), is of significant relevance. A meta-analysis reports a large within-group effect size for iCBT-I (Hedges's $g = 0.86$) for self-reported insomnia severity (16). This effect size was not found to be significantly different than effect sizes in individual or group CBT-I. A number of studies have shown the efficacy of iCBT-I in comparison with control groups receiving less active treatments (i.e., wait-list, sleep education, etc.) as summarized in several meta-analyses.

Internet-based CBT-I (Sleepsy[©]) consists of interactive educational material divided into eight modules and explaining homeostatic and circadian mechanisms of human sleep

regulation, the pathogenesis of CI, and its daytime consequences. In this study we aim to confirm effectiveness of this method in the clinical sample in moscow university clinic.

Both pharmacotherapy, CBT-I (or BBT-I) and their combinations produce treatment response only in 60-67% of patients and remission only in 42-55%. A reasonable way to improve the clinical effectiveness is determining the target group of patients that benefits most of iCBT-I. Some studies have shown that efficacy of CBT-I is related to the severity of maladaptive cognitions and behavior. As there is not much knowledge about predictors of iCBT-I treatment efficacy, in this trial, we will deliberately analyze psychometric, anamnestic and sleep characteristics which may act as predictors of CBT-I, which may also be relevant in iCBT-I. Specifying predictors of effectiveness of iCBT-I will give the opportunity to develop more individualized therapeutic decision-making procedure and will be important for economic reasons. In the longer term, obtaining of portrait for patient who benefit from iCBT-I will give us cues to understanding insomnia in whole and its subtypes.

It would be the first implementation of on-line behavioral treatment for insomnia in Russia and the first attempt to develop online materials for chronic insomnia treatment which would simplify the insomnia treatment improve patient adherence. In view of a huge demand of specialists in CBT-I development and approbation of this program will fill this gap in clinical practice. All the participants will have access to care as usual (CAU), which let us reconstruct real clinical situation along the whole course of the study. To our knowledge, this is one of the first studies considering iCBT-I in clinical settings.

1.2. PREVIOUS CLINICAL APPLICATION

Structure of the investigated treatment course Internet-based CBT-I (Sleepsy[©]) is based on the already established program iSLEEP – internet-based self-help against insomnia that was already tested in previous study in Bern Universitz, Switherland. Short-term effectiveness of iCBT-I was high with effect size from median to large. The longest follow-up period in the studies of iCBT-I was 3 years. After this period there was no difference in the primarz outcomes between intervention and control group, but participants of intervention group used sleep aids significantky less than control. Moreover, there were no adverse events throughout the follow-up

Since the overwhelming majority of iCBT-I randomized controlled trials (RCTs) were conducted in research settings with recruitment via internet and advertisement, it is unclear if the promising results from efficacy studies can be transferred to routine clinical practice. For this study participants will be recruited from the doctor's office to ensure proper diagnostics and exclusion of other diseases affecting depth and length of sleep. It may be that patients, referred to iCBT-I directly from doctor's office, have active and more severe sleep complaints, and therefore are more motivated to benefit from the treatment

2. Aim of the study

Aims:

1. to investigate clinical effectiveness and cost-effectiveness of the internet-based CBT-I program Sleepsy in comparison with care as usual (CAU) among patients with CI recruited from clinical settings.

2. to investigate predictors of treatment outcome by analysis of baseline characteristics.

Tasks:

[figure not shown]
- Baseline assessment of recruited participants;
- Randomization;
- Treatment of intervention group by means of iCBT-I course;
- Post-treatment assessment of all participants;
- Follow-up assessment of all participants;
- Comparison of primary and secondary outcomes in intervention and control groups;
- Treatment of control group by means of iCBT-I course;
- Post-treatment assessment of control group participants;
- Statistical analysis of response predictors.

Hypothesis

- iCBT-I is more effective and cost-effective than CAU in clinical settings
- The analysis will help us identify the typical sleep pattern and obtain psychological portrait of those who benefits from behavioral treatment

3. STUDY DESIGN

- a) The proposed study is a multicenter parallel-group add-on superiority RCT comparing an active treatment condition (iCBT-I plus CAU) to CAU alone.

After signing the IC form, participants will receive an e-mail with the link to the Qualtrics Survey Software (Qualtrics, Provo, UT, USA), where they complete baseline assessment and receive the individual allocation code. On completion of baseline measures, subjects will be automatically assigned by the randomization function of Qualtrics Survey Software to either iCBT-I plus CAU or CAU group using single block randomization. Neither participants nor referring specialist nor the research team have foreknowledge and/or control over randomization and the allocation procedure. Following randomization, the participants will receive an automated email regarding their group allocation and a description of future steps. In case they were allocated to the treatment group, their individual code will provide an access to the iCBT-I program.

Participants in the control group will get access to the iCBT-I program after the 5-month follow-up (3 months after post-assessment) provided they completed the follow-up assessment and still fulfill eligibility criteria. In this group, an additional assessment will be conducted eight weeks after providing access to the CBT-I program to enlarge the sample for the analysis of outcome predictors.

The research team, except the trial coordinator, will be blind to allocation. Coding allocation form, along with the participant's real name and address noted in the IC form, will be stored in the password-protected computer of the trial coordinator. Participants will not be blind to treatment allocation and will receive information about their randomization outcome via email. Questionnaires and sleep diaries will be completed entirely online under the participant's individual code.

3.1.OUTCOMES

3.1.1. The primary endpoint of the present study is the change of Insomnia Severity Index (ISI) from pre- to post-treatment and at follow-up.

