7.1. INCLUSION CRITERIA

1. Age between 18 and 80 years
2. Sleep disorder matching CI criteria (International Classification of Sleep Disorders-3) — assessed by clinical judgement
3. Ability to follow the procedures of the study, fluent Russian language, good access to internet — assessed by self-report

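### Section 3 makes control access to iCBT-I depend on still being eligible at about week 20, which may give unblinded controls a reason to report persistent insomnia on the T2 ISI, part of the primary endpoint

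*Combined protocol and SAP*

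**What the plan says.** All references are to the combined protocol and SAP.

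- **Access for controls.** Section 3 offers the program to the control group after the 5-month follow-up, "provided they completed the follow-up assessment and still fulfill eligibility criteria".
- **Eligibility.** The insomnia criterion in section 7.1 reads "Sleep disorder matching CI criteria (International Classification of Sleep Disorders-3) — assessed by clinical judgement". Sections 7.1 to 7.3 contain no ISI cutoff. The criteria scored from questionnaires are the BDI-II and BAI limits and the BDI-II suicidality score.
- **Blinding.** Section 3: "Participants will not be blind to treatment allocation and will receive information about their randomization outcome via email". It adds that "the participants will receive an automated email regarding their group allocation and a description of future steps". Whether those steps mention the eligibility condition is not visible.
- **Outcome.** Section 3.1.1 defines the primary endpoint as "change of Insomnia Severity Index (ISI) from pre- to post-treatment and at follow-up". On data collection, section 3 says: "Questionnaires and sleep diaries will be completed entirely online under the participant's individual code".
- **Timing.** Section 3.2 puts T1 at week 8, T2 at week 20 and, for controls, T3 at week 28.
- **Other statements of access.** Section 3.2 mentions only completion of the follow-up before the offer. Section 9.1 says that controls get access after follow-up and states no condition. The task list in section 2 also has no eligibility condition.

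**The concern.** The condition applies to one arm only, because the iCBT-I arm already has the program. It takes effect at about the time when controls complete a self-reported measure that belongs to the primary endpoint. A control who wants the program and knows of the condition could reasonably think that reporting improvement would forfeit it.

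A higher reported T2 ISI among controls would look the same as a treatment effect that lasts to week 20. A responder comparison (ISI drop of more than 7 points, section 3.1.2) would be exposed in the same way if it were made at T2. Section 9.2 plans no sensitivity analysis aimed at this.

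The randomised comparison ends at T2 and gains nothing from the condition. By sections 3 and 9.1, delayed access serves to enlarge the predictor sample.

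**Working it through.** **1. The plan's own figure, and which time point it concerns.** Section 9.1 gives 110 patients for d = 0.35 at post-treatment, alpha 0.05 and power 0.95, using a repeated-measures ANOVA in G*Power. The number of measurements m and their correlation rho are not stated. I assumed the within-between interaction with m = 2, rho = 0.5 and f = d/2 = 0.175.

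- lambda = f² × N × m / (1 − rho) = 0.030625 × 110 × 2 / 0.5 = 13.475
- Power = 0.953, and 110 is the smallest even N that reaches 0.95.

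So 110 reproduces. Two measurements fit a pre-to-T1 comparison, as section 9.1 says. The figure is not in dispute. It shows that the sized comparison is at T1, before the access condition applies.

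**2. When access falls.** T3 is at week 28 (section 3.2) and also eight weeks after access (section 3). 28 − 8 = 20, so access falls at about week 20, the time of T2. Section 3.2 lists no separate visit then. The insomnia measures it schedules at T2 are the ISI and the sleep diary.

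**3. Possible size.** The documents give neither an ISI standard deviation nor a rate of overstatement. Everything in this step is an assumption.

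- Shift in control mean = share overstating × points overstated
- Spurious d = shift / SD

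| Share | Points | SD | Shift | d | d / 0.35 | Two-sided type I error at T2 |
|---|---|---|---|---|---|---|
| 10% | 2 | 5 | 0.2 | 0.04 | 11% | 0.055 |
| 30% | 2 | 5 | 0.6 | 0.12 | 34% | 0.096 |
| 30% | 4 | 5 | 1.2 | 0.24 | 69% | 0.242 |

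The last column is 1 − Φ(1.96 − d/s) + Φ(−1.96 − d/s), with s = √(2/55) = 0.191 in SD units. It assumes 55 analysed per arm and a change score with correlation 0.5, so that the SD of change equals the SD of the score. For the middle row d/s = 0.12/0.191 = 0.63.

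Wider assumptions (10-50% of controls, 1-4 points, SD 4-6) give d from 0.1 × 1/6 = 0.02 to 0.5 × 4/4 = 0.50. The 0.35 is only a yardstick here, since section 9.1 sets it for T1.

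**The case against.** The strongest reply is that the link from the T2 ISI to access is not in the documents. Chronic insomnia is judged clinically and no ISI threshold applies. Section 3.2 lists instruments, and it shows no clinic visit at T0 either, although diagnosis at entry is made in the doctor's office. Section 4.1 expects further doctor visits during the study. A reader might infer that the T2 questionnaires are in practice the re-check. The documents do not support that; they leave the method open. What remains is that the condition itself is stated, access falls at about T2, and nothing separates T2 answers from it.

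Four further points have weight.

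- **Knowledge.** The incentive needs controls to know of the condition, and this cannot be seen. Controls whose insomnia persists need not exaggerate, and recovered controls may not want the program. This limits the share affected.
- **Direction.** A reader might infer that any distortion must favour iCBT-I. The same clause bars high BDI-II and BAI scores, so it could also push reported distress down. The direction is likely for ISI but not certain across self-reports.
- **Detection.** It would be too strong to call the effect undetectable. The ungated T1 ISI allows a look at the T1-to-T2 change in controls, and care use is recorded in both arms (sections 3.1.2 and 4.1).
- **Deferred care.** A reader might infer that controls become a wait-list. Waiting would come largely from the promise of later access, with or without the eligibility condition. Deferred care would also lower control costs, so its net effect on the cost-effectiveness ratio is unclear.

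**Conclusion.** The point holds as a moderate design weakness at T2. Access conditional on current chronic insomnia coincides with an unblinded, self-reported primary measure, and only controls face the condition. The likely direction on ISI favours iCBT-I.

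The size is unknown. The range d = 0.04 to 0.24 rests wholly on an assumed share of 10-30%, an assumed overstatement of 2-4 points and an assumed SD of 5. It also requires that controls know of the condition and believe that their T2 answers matter.

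A reader might infer that the trial's main result is compromised. The documents do not support that: the sample size rests on T1, which is not the gating assessment, and nothing shows that overstatement occurs.

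**What to change.** 1. Reconcile the access condition in section 3 with sections 3.2 and 9.1, which do not carry the eligibility requirement. At the same time, reconcile the source of the controls' T2 diary (Qualtrics in section 3.1.2, the Sleepsy program in section 3.2), because it bears on when controls first enter the program.
2. State in section 3 and in the allocation e-mail that T2 ISI and sleep-diary answers are not used to decide access. The requirement to complete T2 can stay: it does not depend on what is answered, and it supports retention.
3. Leave the safety-related criteria in sections 7.2 and 7.3 as they stand.
4. In section 9.2, use whether a control still meets the chronic insomnia criteria at T2 only as a filter or covariate in the predictor analysis.

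This separates T2 answers from access and is not advice on who should be treated. It costs a sentence in section 3, a sentence in the e-mail and a line in section 9.2. The sample size does not change. Some improved controls may be offered the program and would be left out of the predictor set. The promise of delayed access remains, with any waiting effect on usual care, and this change does not remove it.

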3.1.2. Secondary outcomes

- 1) Subjective Sleep Characteristics will find reflection in the sleep diary in such variables as sleep onset latency (SOL), total sleep time (TST), sleep efficiency (SE), calculated as TST/time in bed × 100, wake after sleep onset (WASO), and number of awakenings. In order to obtain these data we will ask control group participants to fill in online sleep diary in Qualtrics for one week starting at time-point T0 (after randomization), T1 and T2. iCBT-I + CAU group participants will fill it only at time-point T2 since online sleep diary is integrated into the iCBT-I program and we can use its data for the treatment and post-treatment period.
- 2) Severity of Insomnia. ISI is important not only as primary measure of treatment effect but also as possible outcome predictor and response criterion. To evaluate it, we will use baseline ISI score and ISI score at the other timepoints. The response criterion is determined as decrease of the ISI score of more than 7 points compared to baseline.
- 3) Daytime symptoms of insomnia are often represented by sense of fatigue, sleepiness, and headaches. The fatigue severity will be evaluated by the Fatigue

Severity Scale (FSS), a disorder nonspecific 7-item scale which measures the severity of fatigue and its effect on a person's activities and lifestyle. Short-form survey (SF-12) version 1.0 is a non-specific scale assessing quality of life by means of eight subscales (vitality, physical functioning, bodily pain, general health perceptions, physical role functioning, emotional role functioning, social role functioning, mental health). Sleepiness as one of the most often reported symptoms of CI will be evaluated by the Epworth Sleepiness Scale (ESS)

- 4) Anxiety and depressive symptoms will be assessed with the Beck Anxiety Inventory (BAI) and the Beck Depression Inventory (BDI-II). Both of them comprise 21-question with a 4-point Likert scale and ranging answers from 0 to 3, yielding a total score ranging from 0 to 63. A BAI total score higher than 25 corresponds to severe anxiety, and a BDI cutoff higher than 28 indicates severe depression.
- 5) Behavioral Perpetuating Factors. One of the leading perpetuating factors of insomnia is poor sleep habits that can be assessed by the Sleep Hygiene Index, a 13-question questionnaire, yielding a total score ranging from 13 to 65. We have translated it into Russian according to a forward and backward translation procedure.
- 6) Cognitive Perpetuating Factors will be assessed by the Sleep Locus of Control Questionnaire (SLC) and Dysfunctional Beliefs and Attitudes About Sleep Scale (DBAS). Both questionnaires were validated in Russian.
- 7) Description of personal characteristics may play an important role in predicting treatment outcome. For this purpose, we intend to use the Personality Inventory for DSM-5 faceted brief form (PID-5-FBF) 100-item self-report inventory designed to assess the 25 pathological personality trait facets and the five domains based on the dimensional trait model (DSM-5 Section III). For translation the questionnaire we used forward and backward translation procedure.
- 8) In order to evaluate the cost-effectiveness of iCBT-I, we will collect information concerning healthcare consumption and productivity losses for the study period using the Trimbos Questionnaire for Costs associated with Psychiatric illness (TiC-P) consisting of two parts. The first part consists of 14 questions on the volume of health care uptake including names, dosage, and frequency of use of medications for insomnia treatment; the second part is represented by the Short Form-Health and Labor Questionnaire (SF-HLQ), an instrument to collect data on productivity losses (presenteeism and absenteeism) due to health problems. For the proposed study questionnaire was translated into Russian.
- 9) During the intervention, we will assess adherence by recording of the number of completed modules, total time spent on the iCBT-I website, time spent on each module, number of completed sleep diaries and usage of the support. Time spent on the website will be measured by means login/logout data and by keeping an activity journal.

-
- 10) In order to analyze such important outcome predictor as patients beliefs about the expected treatment success and to evaluate between-group difference with regard to this factor, we include in baseline assessment one adapted question of Credibility/Expectancy Questionnaire: "At this point, how successfully do you think this treatment will be in reducing your insomnia symptoms?" at scale from 1 to 9.
- 11) User Satisfaction. After completion of the iCBT-I course participants will be requested to fill in feedback questionnaire developed for this study. It includes 5-point Likert scale, from 1 (very poor/not at all useful) to 5 (very, good/very useful) on questions about satisfaction or dissatisfaction with the treatment, and open questions about possible negative effects of the intervention if any: deterioration of insomnia symptoms, adverse effects, novel symptoms; and about improvement suggestions, what participants like most, if they would recommend it to a friend with insomnia.
- 12) The System Usability Scale (SUS) is the 10-item non-specific questionnaire used to collect a user's subjective rating of a product's (products, websites, applications, hardware, or software) usability and learnability. Each item is scored on a scale of 0 ("strongly Disagree") to 5 ("strongly Agree").
- 13) General information will be requested at baseline: age, sex, education, social status, duration of CI, sleep aids if any.

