9. STATISTICAL ANALYSIS

9.1. SAMPLE SIZE CALCULATION

We aim to detect a small to medium between-group effect size (Cohen's d) of 0.35 at post-treatment. The chosen effect size is reasonable since CAU being an active alternative treatment may decrease between-group outcome differences and a smaller effect size was considered to be irrelevant from a clinical point of view. Based on a-level of .05 and a power of .95 using a single-level repeated measures ANOVA power analysis with G*Power, the sample size needed is approximately 55 participants per group and 110 for the total sample. Our secondary aim is to find outcome predictors within participants who complete iCBT-I. In order to enlarge this sample, participants from the CAU group will get access to the iCBT-I program after the follow-up period.

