9.2. STATISTICAL ANALYSIS OF EFFECTIVENESS

The main analyses will be conducted on the intention-to-treat sample. Clinical effects of treatment will be evaluated using mixed-model repeated-measures analyses where the pre-post comparisons of all outcome measures will include time as a within-group variable and the condition as a between-group variable. An incremental cost-effectiveness ratio (ICER) will be calculated to obtain the additional costs of iCBT-I in comparison with control condition. Cohen's d will be reported for all within-between comparisons based on estimated means and the pooled standard deviation from the observed means at pre- and posttreatment. To test significance of the difference between the number of responders in each treatment condition, we will use χ^2 -test. Regression analyses will be used to identify predictors of treatment outcome. We will test models using Akaike/Bayesian Information Criteria to select an optimal model with predictors of treatment outcome.

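### Baseline ISI is a candidate predictor of an outcome apparently measured as a fall from that same score, so in a treated-only analysis it will usually seem to predict benefit even if everyone benefits equally

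*Combined protocol and SAP*

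**What the plan says.** Section 3.1.2, item 2 gives ISI three roles: "ISI is important not only as primary measure of treatment effect but also as possible outcome predictor and response criterion". It continues: "To evaluate it, we will use baseline ISI score and ISI score at the other timepoints". The response rule follows: "The response criterion is determined as decrease of the ISI score of more than 7 points compared to baseline". Section 3.1.1 sets the primary endpoint: "The primary endpoint of the present study is the change of Insomnia Severity Index (ISI) from pre- to post-treatment and at follow-up".

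Section 2 (Aim of the study) has as its second aim "to investigate predictors of treatment outcome by analysis of baseline characteristics" and lists the task "Statistical analysis of response predictors". Section 9.1 fixes the population: "Our secondary aim is to find outcome predictors within participants who complete iCBT-I". Controls who receive the program after follow-up are added to enlarge that sample.

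Section 9.2 says only: "Regression analyses will be used to identify predictors of treatment outcome", with the model chosen by AIC or BIC. It gives no dependent variable, no baseline adjustment and no interaction with arm for these regressions, and it does not mention regression to the mean.

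**The concern.** If the outcome is the fall in ISI, or response defined by that fall, the T0 score is both the predictor and part of the outcome. A patient who happens to score high on the day of T0 will tend to score lower later whatever the treatment does, and so shows a larger fall. Because the analysis is confined to treated completers, no concurrent control group is available to show how much of that fall would have happened anyway.

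The predictor aim is meant to describe who benefits from iCBT-I, and the Background says that predictors should support individualised treatment decisions. A finding that more severe insomnia predicts response could be reported and used in that way although it follows largely from how response is defined.

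**Working it through.** **Inputs from the documents.** Response is a fall of more than 7 ISI points. The primary endpoint is change in ISI. The predictor sample is iCBT-I completers: up to 55 from the treated arm, and at most 110 once controls are added. The sample size uses d = 0.35, alpha 0.05, power 0.95 and N = 110.

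**Inputs assumed, because the documents give none.** ISI mean 17 and SD 4.5 at T0, the same SD after treatment, the same true fall of 6 points for everyone, scores rounded and held to 0–28, and a pre-post correlation ρ between 0.4 and 0.9.

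**1. The plan's own figure.** Take a repeated-measures ANOVA, within-between interaction, two groups, two time points, f = d/2 = 0.175 and ρ = 0.5. The noncentrality is f² × N × 2/(1 − ρ) = 0.030625 × 110 × 4 = 13.475, and power at N = 110 is 0.953. So N = 110 is reproduced. The plan does not state ρ; with the other settings held, 0.3 would need 152 and 0.7 would need 66. A ρ of 0.5 is therefore compatible with the plan but not documented.

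**2. Size of the coupling.** Let B be the baseline score and P the post-treatment score, both with variance σ², and let the true benefit be the same for all.

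- cov(B, B − P) = σ²(1 − ρ)
- var(B − P) = 2σ²(1 − ρ)
- corr(B, B − P) = √((1 − ρ)/2)

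This is 0.55 at ρ = 0.4, 0.50 at 0.5, 0.39 at 0.7 and 0.22 at 0.9. With unequal SDs, k = SD post/SD pre, the correlation is (1 − ρk)/√(1 + k² − 2ρk). At ρ = 0.7 it is 0.61 for k = 0.8 and 0.14 for k = 1.25, and it vanishes when ρk = 1 (k about 1.43).

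**3. What this does to response rates.** With an assumed SD of 4, a fall of 7 for everyone and ρ = 0.5, a patient 1 SD above the mean has an expected fall of 7 + 0.5 × 4 = 9, with residual SD 4 × √0.75 = 3.46. A fall of 8 or more (cut at 7.5) then has probability Φ((9 − 7.5)/3.46) = 67%. The same sum gives 44% at the mean and 24% at 1 SD below it. At ρ = 0.7 the three figures are 60%, 43% and 28%.

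**4. How often baseline ISI is falsely significant (p < 0.05), equal benefit for all.**

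| Setting | Fall in ISI | Response |
|---|---|---|
| n = 80–110, ρ 0.4–0.7 | 95–100% | 78–100% |
| n = 80–110, ρ 0.9 | 54–69% | 33–42% |
| n = 55, ρ 0.5 | 98% | 89% |
| n = 55, ρ 0.7 | 86% | 64% |
| n = 55, ρ 0.9 | 39% | 27% |

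The n = 55 rows use mean 18, SD 4 and a fall of 7. An arm with no mean change at all shows the same effect for the fall: 98% at ρ = 0.5 and 85% at ρ = 0.7, n = 55.

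**5. Other candidate predictors.** Take a covariate correlated 0.6 (assumed) with the stable part of severity and unrelated to the day-to-day part. It is significant for the fall and for response in about 5% of trials, the nominal rate. Put the same covariate into a treated-only model of post-treatment ISI with T0 ISI forced in, and it is falsely significant in 60–82% of trials at n = 80–110 and ρ 0.4–0.7. The noisy T0 score adjusts only partly for severity, and the covariate picks up the remainder. A covariate that shares the transient part of T0 does correlate with the fall (0.19–0.27 in one run).

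**6. A test that holds its level.** A baseline-by-arm interaction on T1 ISI, 55 per arm and a constant treatment effect, is significant in 4–6% of trials. Regression to the mean acts alike in both randomised arms and cancels.

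**The case against.** **The outcome is inferred.** Section 9.2 speaks only of treatment outcome, and "To evaluate it, we will use baseline ISI score and ISI score at the other timepoints" would also fit a regression of T1 ISI on baseline ISI. This stands: a reader might infer that the plan commits to the fall as the outcome, and it does not. But response and change are the only ISI outcomes that the plan defines, and section 2 names response. If post-treatment ISI were used instead, a high baseline would predict a worse score, which is no evidence of differential benefit either.

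**A false finding is not certain.** The size depends on ρ and on the SD ratio, neither of which is documented. It is clearly weaker at ρ = 0.9 and can disappear if scores spread out enough after treatment. This stands as a limit, although a constant benefit does not itself widen the SD. Selection is also by AIC or BIC rather than p-values. For one term, AIC retains it when the likelihood-ratio statistic exceeds 2 (p below 0.157). BIC requires ln 80 = 4.38 to ln 110 = 4.70 (p below about 0.036 to 0.030). So AIC is more lenient than the 5% used above and BIC somewhat stricter.

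**Other scales need not be affected.** It is tempting to say that DBAS, BDI and FSS inherit the artefact whenever baseline ISI is left out. Step 5 shows that this is so only if they share the transient part of the T0 score. That is plausible for questionnaires completed at the same assessment, but nothing in the documents establishes it.

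**Patients with a T0 score of 7 or less cannot respond.** This is true, and section 7.1 sets no minimum ISI. Under the assumed distribution, though, it concerns about 1.7% of patients: Φ((7.5 − 17)/4.5) = Φ(−2.11).

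**Conclusion.** The point holds as a conditional one. If the predictor outcome is the ISI fall or response, as the plan's definitions suggest, baseline ISI in the treated-only analysis will usually look like a predictor of benefit when benefit is the same for all. It is near certain for the fall at ρ of 0.4–0.7 with 80 or more patients, less so for response, and roughly a third to two thirds at ρ = 0.9. These figures rest on assumed SDs, equal spread before and after, and ordinary within-person variation; with perfectly stable, error-free scores there would be no effect.

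Two wider readings are not supported. The randomised primary comparison, and the test of responder numbers between arms, are not biased by this, because the effect is common to both arms. Nor do the documents contain any rule that would deny treatment to milder patients; the risk lies in how a secondary finding might be used. The matter should be settled in wording before the predictor analysis is run.

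**What to change.** In section 3.1.2, item 2 and section 9.2:

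- State that baseline ISI will not be selected or interpreted as a predictor of benefit in the treated-only regressions.
- Base any claim about severity, and preferably any claim about who benefits, on a baseline-by-randomised-arm interaction on T1 ISI, adjusted for T0 ISI, in all randomised patients. Report it as exploratory, because N = 110 was not sized for it.
- Name the dependent variable of the treated-only regressions and describe their results as prognostic.
- If that variable is post-treatment ISI adjusted for pre-treatment ISI, add the unadjusted change-score model as a sensitivity analysis. Forcing in pre-treatment ISI is not a full cure: as step 5 shows, it can make covariates tied to stable severity look predictive.

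This needs no new data. The cost is a little more analysis, an interaction test with low power, and giving up a statement about baseline severity from the treated-only models.
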